8.2.2.5 Sample Size Calculations

A total sample size of 600 is considered sufficient to detect an average treatment difference of 0.13 in mean change in the QNPZ-8 scores from baseline, where the treatment difference is averaged over the 4, 8, and 12 month visits in the first year and annual visits thereafter, with a power of 80% at a 5% significance level. The difference of 0.13 in mean change in the QNPZ-8 scores would not be clinically meaningful for an individual participant but would be clinically meaningful for a participant group. Table 3 displays the sample sizes necessary under several scenarios. The sample size of 600 assumes a standard deviation of 0.7 for change in QNPZ-8 scores from baseline to any follow-up visit and is inflated by 10% to account for missed visits and loss to follow-up. With this sample size, a treatment difference of 0.1 would be detected with 58% power.

The sample size calculations were performed for a balanced design, assuming that the QNPZ-8 scores follow a longitudinal mixed model with exchangeable within-participant correlation structure and normally distributed random effects. The correlation structure implies that the between-participant standard deviations of change in QNPZ-8 scores from baseline to a given follow-up visit are equal through follow-up within each treatment group. For simplicity, the SD in Table 3 is expressed as standard deviation of change from baseline to any follow-up visit. The model used for the sample size calculations assumes that every participant completes the month-48 visit, as an approximation for the projected mean follow-up of 4.5 years in the main START study.

Table 3. Total Sample Size for Detecting Average Treatment Differences Between the Early and Deferred Groups in Mean Change in QNPZ-8 Scores from Baseline, Averaged over Months 4, 8, 12, 24, 36, and 48; power 80 %, significance level 5%

Difference Early vs. Deferred	Total N (N inflated by 10%)			
	SD=0.5	SD=0.6	SD = 0.65	SD = 0.7
$\Delta = 0.10$	474 (521)	682 (750)	798 (878)	926(1019)
$\Delta = 0.13$	282 (310)	404 (444)	474 (521)	550 (605)
$\Delta = 0.15$	212 (233)	304 (334)	356 (392)	414 (455)

The assumption of SD=0.7 for the standard deviation of the *change in QNPZ-8 scores* from baseline was based on the following considerations.

- a. In the SMART study, QNPZ-5 scores were obtained at baseline and month 6 for 258 participants. The QNPZ-5 scores were based on four of the QNPZ-8 tests, excluding the HVLTR, Semantic Verbal Fluency, and the WAIS-III Digit Symbol tests, plus the Timed Gait test. The standard deviation of change in QNPZ-5 scores (pooled across the two treatment groups) was 0.52, with a 95% confidence interval of 0.48 – 0.57. The value of SD=0.7 was chosen conservatively to guard against model misspecification, including misspecification of the within-participant correlation structure. Also, the somewhat different composition of the neuropsychological test battery compared to the QNPZ-5 may result in a different, possibly higher SD of change for the QNPZ-8.
- b. In a different study, four neuropsychological tests were administered at baseline and month 12, including the Grooved Pegboard, Finger Tapping, Timed Gait, and the Digit Symbol Modalities tests. QNPZ-4 scores were calculated from the standardized test results. The standard deviation of changes in QNPZ-4 scores from baseline to month 12 was 0.7, 95% confidence interval of 0.6 – 0.9 in 108 HIV-infected patients ([name], personal communication).

The protocol team will monitor the standard deviation of change in QNPZ-8 scores and the within-participant correlation structure, pooled across treatment groups. Sample size will be recalculated concurrently with the sample size recalculation for the main START study.

8.2.2.6 Sample Size, Enrollment and Site Selection

Enrollment and Site Selection

Enrollment into the Neurology substudy is planned to start concurrently with the main START study. The Neurology substudy aims to co-enroll participants from a limited number of sites and to co-enroll a high proportion of eligible participants at these sites. Limiting the number of participating sites makes it easier to standardize the administration of the neuropsychological tests and also is more cost effective.

It is planned to assess feasibility and re-calculate sample size for the Neurology substudy concurrently with the main START study, taking into account the observed standard deviation of change in QNPZ-8 scores and the expected duration of the main study.

8.2.2.7 Participant Selection

A total of 600 participants will be enrolled at selected sites that are geographically diverse and ensure a demographically diverse population. At these sites, it is planned to co-enroll a high proportion of the eligible START study participants.

Inclusion Criteria

- Simultaneous co-enrollment in the START study
- Signed informed consent (see [Appendix A6](#))
- Age \geq 18 years

Exclusion Criteria

Participant is unable to perform necessary tests in the protocol, in the clinician's judgment.

8.2.3 Clinical Management Issues

8.2.3.1 Administration of the Neuropsychological Tests

The research staff who will administer the neuropsychological tests will be well trained in the standardized format in which these tests should be given. Research staff will participate in follow-up training to ensure correct administration of the tests as necessary. The tests are simple to administer and the total time per study visit will take about 50 minutes.

Table 4. Expected Time Needed for Tests and the CES-D

Test	Time
Grooved Pegboard (both hands)	8 min
Color Trails 1 and 2	3-8 min
WAIS-III Digit Symbol	5 min
HVLT-R, Learning	10 min
HVLT-R, Delayed Recall	3-5 min
Semantic Verbal Fluency	3 min
Finger Tapping (Both Hands)	8 min
CES-D	5 min
Total	45 - 52 min

The ethos that will underpin the training of the clinicians who will administer these tests is that the tests are serving as measures of the health of the participants' neurocognitive and motor performance. Thus, any discussions about these tests with the participants should impart the notion that we are seeking to define their neurocognitive health rather than their neurocognitive impairment.

All efforts will be made to make the participants feel comfortable and relaxed during the testing. If participants become fatigued or anxious during the testing they will be given an opportunity to rest and the testing may be ceased prematurely at the participant's request. During the administration of the tests, participants will be positively encouraged irrespective of their performance on the tests.

The test scores for the individual tests will be collected on standardized case report forms. The z-scores, ADS scores, and CES-D scores will be calculated at the INSIGHT statistical center. Calculated test scores will not be available in real-time, and will not be returned to the clinical sites. Participants in the Neurology substudy should continue to receive screening for cognitive impairment as per local standard of care. If concerns arise during the administration of tests or the CES-D questionnaire, it is recommended that participants be referred for diagnosis and treatment according to local guidelines.

8.2.3.2 Study Withdrawal

Participants may withdraw from the study at any time at their request, as described in section 4.5 of the START protocol. A participant can withdraw from the Neurology substudy and still be followed in the START study. If a participant withdraws from the main START study, the participant will be withdrawn from the Neurology substudy.

Otherwise, participants should be followed according to protocol, even if a participant chooses not to adhere to the treatment assignment or data collection schedule.

8.2.4 Evaluation

8.2.4.1 Data Analysis

All analyses comparing the treatment groups will be by intent to treat. Comparisons between treatment groups will be stratified by geographical area of enrollment, unless sample sizes are too small or stratification is inappropriate for other reasons.

Primary Analysis

For the primary objective, mean changes in QNPZ-8 scores from baseline will be compared between the early and deferred groups using all measurements through follow-up in a longitudinal mixed-effects model, stratified by geographical area of enrollment. The model will also include “month of visit” as categorical covariate, to adjust for a possible learning effect that would occur equally in both treatment groups.

Secondary Analyses

For each of the component tests of the QNPZ-8, mean changes from baseline in unadjusted test scores and in z-scores will be compared between the early and deferred groups using all measurements through follow-up in longitudinal mixed-effects models. The slopes in these endpoints through year 1 and through follow-up will also be compared between treatment groups, using longitudinal mixed-effects models.

Additionally to the standard longitudinal mixed-effects models that assume Gaussian distributions for the random effects, changes in tests scores through follow-up will be compared between treatment groups using O’Brien’s rank-sum test for multiple endpoints.⁸⁶ The two treatment groups will also be compared for changes in test scores from baseline to last visit, and for area under the curve from baseline through follow-up for the QNPZ-8 and each of the component tests.

The early and deferred ART arms will be compared for changes in test scores (QNPZ-8, z-scores, and unadjusted test scores) within subgroups of participants defined by demographics (age, sex, race/ethnicity, education, occupation, employment status, income, urban or rural area of residence), geographic location, CD4+ cell count, HIV RNA level, and other baseline characteristics using longitudinal mixed models. Presence of differential treatment effects across subgroups will be assessed by tests for interaction between subgroup and treatment group indicators in these longitudinal models.

In order to assess presence of a lateral effect on neurocognitive functioning, for finger tapping and grooved pegboard, the interaction between treatment group indicator and indicator for dominant versus non-dominant hand will be assessed in longitudinal models with double-repeated measures (within participant, measures are repeated over time, and across hands). If there is evidence for such an interaction, it will be investigated as to whether it changes over time, for example, by fitting an additional slope parameter. Change in test scores will also be compared between the dominant and non-dominant hands within the treatment groups.

The effect of classes of antiretroviral drugs on neurocognitive functioning will be assessed by comparing the early versus deferred ART treatment effect between subgroups of participants: those whose planned initial ART regimen (determined prior to randomization) contains the drug class under investigation, and those whose planned initial regimen does not contain the drug class. This means, the effect of the drug class will be assessed through the interaction effect between treatment and subgroup indicator. Also, ART regimens will be classified by their estimated level of CNS penetration. To test the hypothesis that higher CNS penetration protects neurocognitive functioning, the interaction effect between CNS penetration and treatment group indicator will be assessed in longitudinal models.

The early and deferred groups will be compared for proportions of participants with neurocognitive impairment using longitudinal models for binary data, for example, generalized estimating equations (GEE). The ADS is an alternative measure of neurocognitive impairment. The early and deferred groups will be compared for changes in ADS using longitudinal mixed models for ordinal data. Subgroup analyses will be performed if sample size is sufficient.

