8.2.2.2 Data Collection

To be collected at baseline (within 60 days prior to randomization), months 4, 8, and 12, and annually thereafter:

- a. The quantitative neurocognitive performance (QNPZ-8) score, derived from a test battery consisting of
 - Grooved Pegboard test
 - Color Trails 1 test

- Color Trails 2 test
 - WAIS-III Digit Symbol test
 - Finger Tapping test
 - Hopkins Verbal Learning test – revised (HVLRT-R), Learning and Delayed Recall
 - Semantic Verbal Fluency test (category fluency)
- b. Center for Epidemiologic Studies Depression Scale (CES-D), a tool to screen for depression.

Additionally, to be collected at baseline:

- Extended demographics, including years of education, occupation, employment status, income, and area of residence (urban or rural)

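### The Neurology substudy's primary model compares change in QNPZ-8 without adjusting for baseline QNPZ-8, and so gives up precision that costs nothing to keep

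*Supplement*

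**What the plan says.** Section 8.2.4.1 (Data Analysis, Primary Analysis) states that "mean changes in QNPZ-8 scores from baseline will be compared between the early and deferred groups using all measurements through follow-up". The method is a "longitudinal mixed-effects model, stratified by geographical area of enrollment". Month of visit enters "as categorical covariate, to adjust for a possible learning effect that would occur equally in both treatment groups". No other covariate is named.

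Baseline QNPZ-8 is available. Section 8.2.2.2 schedules the test battery with the words "To be collected at baseline (within 60 days prior to randomization), months 4, 8, and 12, and annually thereafter". Baseline level of neurocognitive function appears in section 8.2.2.3 (items b and c) as a subgroup factor and as a predictor of change. Baseline factors appear again in the association analyses of 8.2.4.1. None of these is the primary treatment comparison.

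Section 8.2.2.5 says that 600 participants are "sufficient to detect an average treatment difference of 0.13 in mean change in the QNPZ-8 scores from baseline", "with a power of 80% at a 5% significance level". The calculation "assumes a standard deviation of 0.7 for change in QNPZ-8 scores from baseline to any follow-up visit" and uses a "longitudinal mixed model with exchangeable within-participant correlation structure". It quotes 58% power for a difference of 0.10. It gives no value for the correlation.

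**The concern.** With a randomized comparison and a baseline measure of the outcome, there are two natural contrasts: the difference in mean change, and the difference in follow-up means adjusted for baseline. Both are unbiased over randomizations. The change score fixes the baseline coefficient at 1. The adjusted analysis estimates it, and under an exchangeable model the best value is r. Forcing it to 1 carries more baseline error into the contrast than is needed.

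In any one trial the same excess appears as sensitivity to chance imbalance. If the arms differ by d at baseline, regression to the mean shifts the expected change-score contrast by -(1 - r)d. Adjustment removes that shift.

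At stake is precision in a substudy that, on its own assumptions, has 80% power for 0.13 and only 58% for 0.10.

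**Working it through.** **Inputs.** From section 8.2.2.5: SD of change 0.7; difference 0.13 (also 0.10); 5% level, taken as two-sided; six listed follow-up visits (months 4, 8, 12, 24, 36, 48); 10% inflation, so 600/1.1 = 545 evaluable. Allocation is 1:1 (section 8.2.2.1). The correlation r is not in the documents and is varied.

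**Formulas.** Let σ² be the variance of QNPZ-8 at one visit, r the common correlation and m the number of follow-up visits. Then SD_change² = 2σ²(1 - r).

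- Change score (mean of follow-up minus baseline): V_c = σ²[(1 + (m-1)r)/m + 1 - 2r] = SD_change² × (1 + 1/m)/2.
- Baseline-adjusted: V_a = σ²[(1 + (m-1)r)/m - r²].
- Ratio: V_a/V_c = 1 - (1 - r)/(1 + 1/m), which is below 1 for every r < 1.

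**The plan's own figure.** V_c does not contain r once SD_change is given, and the plan supplies only SD_change.

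- With m = 5, V_c = 0.49 × 1.2/2 = 0.294. N = 4 × 0.294 × (1.960 + 0.842)²/0.13² gives 548 by the normal approximation and 550 with the t distribution. The t version matches all 12 uninflated entries of Table 3. Power for 0.10 at N = 550 is 0.580, against the stated 58%.
- With the six visits that Table 3 lists, N is 532 (normal) or 534 (t), about 3% lower.

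Either way, the substudy was sized on the unadjusted change score. A baseline-adjusted calculation would have needed r.

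**With baseline added** (SD of change held at 0.7):

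| r | Ratio, m = 6 | Power for 0.13, 545 evaluable, m = 6 | Ratio, m = 5 | Power for 0.13, N = 550, m = 5 | Power for 0.10, N = 550, m = 5 |
|---|---|---|---|---|---|
| unadjusted | 1 | 0.81 | 1 | 0.80 | 0.58 |
| 0.7 | 0.743 | 0.91 | 0.750 | 0.90 | 0.70 |
| 0.8 | 0.829 | 0.88 | 0.833 | 0.87 | 0.66 |
| 0.9 | 0.914 | 0.84 | 0.917 | 0.84 | 0.62 |

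Worked example (m = 6, r = 0.7): V_c = 0.49 × (7/6)/2 = 0.2858, so SE = √(4 × 0.2858/545) = 0.0458, and 0.13/0.0458 - 1.96 = 0.88, which gives power 0.81. Adjusted SE = 0.0458 × √0.743 = 0.0395, and 0.13/0.0395 - 1.96 = 1.33, which gives power 0.91.

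The total N needed for 80% power at 0.13 (m = 5, normal approximation) falls from 548 to 410, 456 and 502 at r = 0.7, 0.8 and 0.9. A simulation with 4,000 runs per setting, at r = 0.5, 0.7 and 0.9, agreed with the variance formulas.

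**A partial bound on r.** Holding SD_change at 0.7 implies σ = 0.90, 1.11 and 1.57 at r = 0.7, 0.8 and 0.9. QNPZ-8 is an average of z-scores scaled to SD 1 in the reference population (section 8.2.2.4), so σ is at most 1 there. If that also holds in START, which is an assumption, r ≤ 1 - 0.49/2 = 0.755. The variance reduction is then at least about 20% with m = 5, and power for 0.13 at N = 550 is at least about 0.88.

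**The case against.** The planned analysis is valid and agrees with its sample size: both use the change-score variance, and the stated 80% power is reached on the plan's assumptions. That stands. This is lost efficiency, not bias. Sensitivity to baseline imbalance is not a second harm, because over randomizations it is already in the standard error.

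No Neurology analysis plan is shown, so the covariate list might be completed there. Section 8.2.2.5 also speaks of scores, not changes, following the mixed model, which leaves room for baseline in the outcome vector. But section 8.2.4.1 names the strata and the covariate, and Table 3 reproduces from the unadjusted variance. Putting baseline in the outcome vector recovers the precision only if both arms share one baseline mean, which is not stated. With separate baseline means it equals the change-score contrast.

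The SD of 0.7 is conservative. The treatment-interruption trial cited in 8.2.2.5 observed 0.52, although a second study there observed 0.7. At 0.52 with N = 550 and m = 5, unadjusted power is already about 0.97 for 0.13 and 0.83 for 0.10. With σ = 1 (r about 0.865) adjustment moves these to about 0.98 and 0.87. So the gain in power may be small, though variance still falls by about 11%. Section 8.2.2.5 also provides for monitoring the SD and correlation and recalculating sample size. That protects power but does not recover the lost precision.

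The figures above concern a Gaussian outcome. They do not carry over to the average deficit score (ADS), which is to be analysed with ordinal models.

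**Conclusion.** The concern holds. The primary model as written omits baseline QNPZ-8, and adding it lowers the variance of the treatment contrast for any r below 1. With the six listed visits the reduction is 26%, 17% and 9% at r = 0.7, 0.8 and 0.9. These figures rest on the plan's exchangeable correlation, complete follow-up among the evaluable participants and, for power, an SD of change of 0.7. The value of r is an assumption, and the gain is modest if r is near 0.9. Using five visits in place of six hardly changes the result. The validity of the planned analysis is not in question. The change is worth making because it improves precision at essentially no cost.

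**What to change.** In section 8.2.4.1, state that the primary mixed model includes baseline QNPZ-8 as a covariate, with its interaction with month of visit so that the baseline coefficient can differ between visits. A model with baseline in the outcome vector and a baseline mean constrained equal across arms would also recover the precision; the text should name whichever is used. Include the corresponding baseline value in the change models for each component test, ADS and CES-D.

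The cost is a line of wording. No new data are needed, and no participant is lost, since a change score already requires a baseline value. Section 8.2.4.2 keeps the protocol team blinded to follow-up data, apart from pooled SDs and correlations, until START closes. The model can therefore be fixed without knowledge of the results. The pooled correlation already being monitored would also replace the assumed r when sample size is recalculated.

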8.2.4.2 Data Monitoring

Data for the Neurology substudy will be monitored by the DAIDS DSMB, and study results will be reviewed simultaneously with the main START study.

The protocol team will monitor the standard deviation of change in QNPZ-8 scores and the within-participant correlation structure of the QNPZ-8 scores, pooled across treatment groups, to adjust the sample size if necessary. Additionally, the standard deviation of change in test scores, pooled across treatment groups, will be monitored for each of the component tests of the QNPZ-8, as one measure to control the quality of test administration and to identify need for re-training. The protocol team will be blinded to all other follow-up data until the closing of the START study.

8.2.5 Human Subjects

This protocol must receive the approval of the participating site's IRB or IEC prior to implementation. All study participants must sign an informed consent form (see sample in [Appendix A6](#)).

8.3 Informed Consent Substudy

8.3.1 Background and Rationale

Informed consent is widely accepted as an integral part of ethical clinical research^{87,88} and includes three distinct elements: (1) disclosure of information to prospective research participants, (2) participant understanding of the information, and (3) a voluntary decision by the participant to enroll in the research. Yet, the goal of well-informed individuals making voluntary choices about research participation is often imperfectly realized. Empirical data suggest that comprehension of important study information, especially side effects and randomization of treatment, although variable, can be unacceptably low.^{89,90,91,92,93,94,95} In addition, some participants do not seem to understand that participation is their choice or that they can leave a study at any time.^{94,96,97,98,99,100} Somewhat paradoxically, as more evidence emerges that comprehension is inadequate, written consent documents have become increasingly long and complex. Legal, ethical, regulatory, and risk reduction authorities have all had a hand in adding language to consent documents in the interests of “protecting” the human participant as well as the research institution or sponsor.

Many agree that long and complex written documents are unlikely to enhance understanding, a goal of informed consent. Some groups have attempted to improve the consent process by improving the readability of consent documents.^{101,102,103,104,105,106} Studies that compared typical consent forms to more simplified designs (usually lower in reading level and sometimes shorter) have found either equivalency between the regular and simplified forms^{101,102,103} or statistically and clinically significant improvements in comprehension with a simpler form.^{104,105} Studies that measured satisfaction found that subjects clearly preferred the simplified forms.^{102,103}

The INSIGHT START study presents an opportunity to compare participant understanding after being randomized to either a standard consent form or a more concise consent form, across a variety of languages and international research sites. The main outcome measure will be prospective participant comprehension of the study specific information, and secondary outcome measures will include participant satisfaction with the consent process, and the resources required for this process. Demonstrating that one form is superior to the other would suggest a new standard or reinforce the current approach to writing consent forms. A demonstration of equivalent results would permit investigators to use the most efficient and easiest of equally effective alternatives.

